6.1.1 Investigational drug

The study treatment begins on Cycle 1 Day 1 with the first administration of capmatinib. All dosages prescribed and dispensed to the participant and all dose changes during the study must

be recorded on the dose administration electronic Case Report/Record Form (eCRF). Refer to [Section 6.7.2](#) for study drug prescribing and administration information.

Table 6-1 Investigational and control drug

Investigational Drug (Name and Strength)	Pharmaceutical Dosage Form	Route of Administration	Supply Type	Sponsor (global or local)
Capmatinib (INC280) 150 mg or 200 mg	Film-coated tablet	Oral use	Open-label bottles	Sponsor (local)

6.1.2 Supply of study treatment

Capmatinib 150 mg or 200 mg will be supplied by the sponsor (Novartis).

Storage conditions are described in the medication label. Medication labels will comply with the legal requirements of the country and be printed in the local language.

During the COVID-19 pandemic that limits or prevents on-site study visits, delivery of IMP directly to a participant's home is generally permitted in the event the Investigator has decided that an on-site visit by the participant is no longer appropriate or possible, and that it is in the interest of the participant's health to administer the study treatment even without performing an on-site visit. Implementation will need to be discussed with Novartis. The dispatch of IMP from the site to the participant's home remains under the accountability of the Investigator. Each shipment/provisioning will be for a maximum of 3-months supply. In this case, regular phone calls or virtual contacts (every 4 weeks or less frequently) will occur between the site and the participant for instructional purposes, safety monitoring, and discussion of the participant's health status until the participants can again visit the site.

6.1.3 Treatment group

All participants in this study will be treated with capmatinib 400 mg orally b.i.d.

A complete cycle of treatment is defined as 28 days of continuous capmatinib treatment.

Participants will be assigned to each cohort based on their biomarker status (either METex14 or high level MET amplification or both). See [Section 3](#) for cohort definitions.

6.1.4 Guidelines for continuation of treatment

For guidelines on the management of common capmatinib associated toxicities and dose modification instructions see Section [Section 6.5](#)

Participants should continue to receive the study treatment until one or more criteria for treatment discontinuation described in [Section 9.1.1](#) are met or until treatment completion has occurred.

6.1.5 Treatment duration

Participants will continue to receive study treatment for a maximum of three years following surgery or until early discontinuation (see [Section 9.1.1](#)). All participants must have an EOT & Safety follow-up visit per the assessment schedule, [Table 8-1](#).

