Purpose and rationale	
The purpose of this study is to determine if neoadjuvant capmatinib followed by surgical resection and adjuvant treatment with capmatinib can improve outcomes in participants with IB-IIIA, N2 and selected IIIB (T3N2 or T4N2) lung cancers with MET exon 14 mutations and/or high MET amplification beyond those achieved with surgery, chemotherapy, and radiation.
 
Capmatinib is an effective MET kinase inhibitor. Coupled with its tolerability, it is an ideal drug to use in the preoperative setting. It has no effects on wound healing and venous thromboembolism. Myelosuppression of any degree is uncommon with capmatinib.

Primary Objective(s)	To determine the major pathologic response (MPR) in resection specimens following neoadjuvant capmatinib in 2 cohorts. Cohort A: MET exon 14 skipping mutation, irrespective of MET gene copy number (GCN); Cohort B: High MET amplification (MET : GCN ≥ 10)
Secondary Objectives	
 • To determine the complete pathologic response following neoadjuvant capmatinib therapy in each cohort • To evaluate safety and tolerability of capmatinib • To assess disease free survival with adjuvant therapy with capmatinib • To assess overall response rate post neoadjuvant treatment with capmatinib in each cohort
Study design	
This is a phase II, two cohort, two stage, study of capmatinib given for 8 weeks prior to surgical resection, followed by three year capmatinib treatment in adjuvant setting and a two year survival follow-up.
 
There will be 2 molecularly defined cohorts enrolling in parallel: Cohort A: MET exon 14 skipping mutations, irrespective of MET GCN or Cohort B: high level MET amplification (MET: GCN ≥ 10). [REDACTED]
 
[REDACTED]

Study population	Newly diagnosed participants with clinical stages IB-IIIA, N2 and selected IIIB (T3N2 or T4N2) lung cancers with MET exon 14 mutations and/or high level MET amplification (MET : GCN ≥ 10).
Key Inclusion criteria	
 1. Histologically confirmed NSCLC stage IB-IIIA, N2 and selected IIIB (T3N2 or T4N2) (per AJCC 8th edition), deemed suitable for primary resection by treating surgeon (T4 tumors with mediastinal organ invasion are not eligible for enrollment).

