2.2 Secondary estimands

No secondary estimands planned in this study.

[figure not shown]
3 Study design

This is a phase II, two-cohort, two-stage, study of capmatinib given for 8 weeks (2 cycles) prior to surgical resection, followed by three years capmatinib treatment in adjuvant setting. Surgery should be performed up to 2 weeks after the last dose of neoadjuvant study treatment. Please contact the sponsor if surgery will be beyond the 2 week window.

There will be 2 molecularly defined cohorts enrolling in parallel: Cohort A: MET exon 14 skipping mutations, irrespective of MET GCN or Cohort B: high level MET amplification (MET: GCN ≥ 10 by FISH or FoundationOne CDx NGS using tumor tissue). [REDACTED]

[figure not shown]
[REDACTED] Participants who have both MET exon 14 skipping mutations and high level

MET amplification (MET: GCN ≥ 10 by FISH or FoundationOne CDx NGS using tumor tissue) will be enrolled into Cohort A. An evaluable subject will undergo the neoadjuvant treatment and undergo surgery with a pathological response report analysis.

After surgery, participants will continue onto 3 years of adjuvant capmatinib therapy, followed by two years of survival follow-up.

Figure 3-1 Study design

*Adjuvant chemotherapy is optional and at the discretion of the treating physician. See section [6.2.1.2](#) for further details.

4 Rationale

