6.2.1.1 Adjuvant chemotherapy

Standard postoperative adjuvant chemotherapy, consisting of a platinum-based doublet for 4 cycles is allowed. For patients receiving adjuvant chemotherapy no more than 26 weeks can elapse between surgery and start of adjuvant capmatinib.

Chemotherapy regimen, dosing, start and stop dates must be recorded in the eCRF.

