6.5.1 Treatment interruption and treatment discontinuation

If the administration of capmatinib is temporarily interrupted for reasons other than toxicity, then treatment with capmatinib may be resumed at the same dose. If the treatment with capmatinib is withheld due to toxicity, the dose modification guidelines in [Table 6-3](#) & [Table 6-2](#) should be followed. In any case, scheduled visits and all assessments (including tumor assessments) should continue to be performed, as described in [Table 8-1](#).

If the treatment with capmatinib is withheld for more than 21 consecutive days (counting from the first day when a dose was interrupted), excluding the surgical and adjuvant chemotherapy

window specified below, then capmatinib should be permanently discontinued. Under exceptional circumstance, when the investigator believes that continuing treatment may still derive clinical benefit for the participant, study treatment may be resumed. However, the investigator must discuss and receive approval from Novartis Medical Lead or designee prior to continuing capmatinib treatment.

Participants who discontinue the study due to a study drug related AE or an abnormal laboratory value must be followed as described in [Section 6.5.2](#).

After the 8 week neoadjuvant treatment with capmatinib, participants are to undergo surgical resection. Participants should undergo within 2 weeks after last dose of neoadjuvant capmatinib. In addition, participants may receive adjuvant chemotherapy prior to re-starting capmatinib at the discretion of the investigator. For patients who do not receive adjuvant chemotherapy no more than 10 weeks should elapse from the date of surgery and the start of adjuvant capmatinib. For patients who do receive adjuvant chemotherapy, see [Section 6.2.1.1](#) for the dosing window. If participants for any reason cannot re-start capmatinib therapy within the specified windows, then study treatment must be permanently discontinued.

Participants who discontinue the study due to a surgery related AE must complete the EOT visit and safety follow-up visit.

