Table 8-1 Assessment schedule

Period	Screening	Treatment		Surgery		Treatment		Follow-up	
		Cycle 1	Cycle 2			Cycle 3 & beyond up to 3 years			
Visit Name	Screening	Treatment C1D1	Treatment C2D1	Surgery	Post-surgery	Treatment C3D1	Treatment C4D1 & beyond	EOT	30 day safety follow up
Days/months	-28 to -1	1	28	Within 2 weeks from last dose of capmatinib ⁶	2 weeks from date of surgery ⁹	10-26 weeks from surgery ³	Every 3 months	when applicable	30 days post last dose of capmatinib
Electrocardiogram (ECG)	X	X ²		If clinically indicated				X	
Pulmonary function tests (PFT)	X ⁴			X ⁵	X				
Hematology blood sample	X	X	X		X	X	X	X	X
Chemistry blood sample	X	X	X		X	X	X	X	X
Coagulation panel	X		If clinically indicated						
Urinalysis (dipstick)	X	X	X			X	X		

Period	Screening	Treatment		Surgery		Treatment		Follow-up									
		Cycle 1	Cycle 2			Cycle 3 & beyond up to 3 years											
Visit Name	Screening	Treatment C1D1	Treatment C2D1	Surgery	Post-surgery	Treatment C3D1	Treatment C4D1 & beyond	EOT	30 day safety follow up								
Days/months	-28 to -1	1	28	Within 2 weeks from last dose of capmatinib ⁶	2 weeks from date of surgery ⁹	10-26 weeks from surgery ³	Every 3 months	when applicable	30 days post last dose of capmatinib								
Prior/concomitant medications	X	X (Continuous from 28 days prior to starting treatment until 30 day safety follow-up or start of new antineoplastic medication (ANP), whichever is sooner)															
Non-drug therapies and procedures	X	X (Continuous from 28 days prior to starting treatment until 30 day safety follow-up or start of new antineoplastic medication (ANP), whichever is sooner)															
Adverse Events	X (Continuous until ≥ 30 days after the last dose of INC280)																
Serious Adverse Events	X (Continuous until ≥ 30 days after the last dose of INC280)																
Serum pregnancy test	S (within 72 hours prior to first dose)							S ¹¹	S ¹¹								
Urine pregnancy test ¹¹			S			S	S										

Period	Screening	Treatment		Surgery		Treatment		Follow-up								
		Cycle 1	Cycle 2			Cycle 3 & beyond up to 3 years										
Visit Name	Screening	Treatment C1D1	Treatment C2D1	Surgery	Post-surgery	Treatment C3D1	Treatment C4D1 & beyond	EOT	30 day safety follow up							
Days/months	-28 to -1	1	28	Within 2 weeks from last dose of capmatinib ⁶	2 weeks from date of surgery ⁹	10-26 weeks from surgery ³	Every 3 months	when applicable	30 days post last dose of capmatinib							
Surgery				X												

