PET-CT (with diagnostic quality CT)	X ¹⁰															
CT/MRI – Chest	X ¹⁰			X, To be performed within 7 days prior to surgery	X, At the initiation of adjuvant therapy (chemotherapy or capmatinib) and every 12 weeks for the first year of treatment, every 26 weeks thereafter ⁷											
Brain MRI	X			If clinically indicated												
Whole body bone scan		If clinically indicated														
Tumor sample from surgery ¹				X												

Period	Screening	Treatment		Surgery		Treatment		Follow-up	
		Cycle 1	Cycle 2			Cycle 3 & beyond up to 3 years			
Visit Name	Screening	Treatment C1D1	Treatment C2D1	Surgery	Post-surgery	Treatment C3D1	Treatment C4D1 & beyond	EOT	30 day safety follow up
Days/months	-28 to -1	1	28	Within 2 weeks from last dose of capmatinib ⁶	2 weeks from date of surgery ⁹	10-26 weeks from surgery ³	Every 3 months	when applicable	30 days post last dose of capmatinib
MPR				X					
Adjuvant chemotherapy ⁸					X				
Study drug administration (capmatinib)		X (continuous twice daily (BID) dosing)				X (continuous twice daily (BID) dosing)			
Antineoplastic therapies since discontinuation of study treatment									X

X = assessment to be recorded in the clinical database or received electronically from a vendor

S = assessment to be recorded in the source documentation only

¹ Lymph nodes might be requested if collected, see [Table 8-6](#) for number of unstained slides.

² pre-dose

³ No more than 26 weeks or 10 weeks can elapse between surgery and start of adjuvant capmatinib for patients who have or have not received adjuvant chemotherapy, respectively.

⁴ Within 3 months before starting neoadjuvant capmatinib

⁵ After neoadjuvant capmatinib but before surgery

⁶ Delay to the surgical procedure beyond 2 weeks is acceptable, but should be avoided. Please contact the sponsor if surgery will be beyond the 2 week window.

⁷ Post-surgery scan schedule to start with initiation of any adjuvant treatment, chemotherapy or capmatinib.

⁸ Standard postoperative adjuvant chemotherapy, consisting of a platinum-based doublet for 4 cycles is allowed. No more than 26 weeks can elapse between surgery and start of adjuvant capmatinib.

⁹ Post-surgery visit to be approximately 2 weeks from date of surgery in alignment with practice guidelines.

¹⁰ Chest CT/MRI or PET-CT (with diagnostic quality CT) is required at baseline.

¹¹ For women of child-bearing potential only

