### 1.1 Study design

[figure not shown]
This is a Phase II, two-cohort, two-stage, study of capmatinib given for 8 weeks (2 cycles) prior to surgical resection, followed by three years capmatinib treatment in adjuvant setting. Surgery should be performed up to 2 weeks after the last dose of neoadjuvant study treatment. Please contact the sponsor if surgery will be beyond the 2-week window.

There will be 2 molecularly defined cohorts enrolling in parallel: Cohort A: MET exon 14 skipping mutations, irrespective of MET GCN or Cohort B: high level MET amplification (MET: GCN  $\geq 10$  by FISH or Foundation One CDx NGS using tumor tissue). 

 Participants who have both MET exon 14 skipping mutations and high-level MET amplification (MET: GCN  $\geq 10$  by FISH or Foundation One CDx NGS using tumor tissue) will be enrolled into Cohort A. An evaluable subject will undergo the neoadjuvant treatment and undergo surgery with a pathological response report analysis. 

After surgery, participants will continue onto 3 years of adjuvant capmatinib therapy, followed by 30 days of safety follow-up.

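### Does Section 6.1.5 stop capmatinib three years after surgery when the rest of the plan gives three years of adjuvant treatment?

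*Protocol*

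**What the plan says.** Section 6.1.5 of the protocol, on treatment duration, states: "Participants will continue to receive study treatment for a maximum of three years following surgery or until early discontinuation". Other places describe the same period differently:

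- Protocol synopsis, study design: "followed by three year capmatinib treatment in adjuvant setting".
- Protocol Section 3: "After surgery, participants will continue onto 3 years of adjuvant capmatinib therapy".
- SAP Section 1.1: "participants will continue onto 3 years of adjuvant capmatinib therapy, followed by 30 days of safety follow-up".
- Protocol Table 8-1, header over the columns that begin at C3D1: "Cycle 3 & beyond up to 3 years".

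Two limits govern the restart of capmatinib. With adjuvant chemotherapy, Section 6.2.1.1 says "no more than 26 weeks can elapse between surgery and start of adjuvant capmatinib". Without it, Section 6.5.1 says "no more than 10 weeks should elapse from the date of surgery and the start of adjuvant capmatinib", and a participant who misses the applicable window must stop study treatment for good. Footnote 3 of Table 8-1 repeats both limits: "No more than 26 weeks or 10 weeks can elapse between surgery and start of adjuvant capmatinib", assigned by chemotherapy status.

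**The concern.** Section 6.1.5 is where a site would look for the stopping point, and its words suggest a ceiling counted from surgery. Three years of adjuvant capmatinib fits under that ceiling only if the drug restarts on the day of surgery, and the protocol allows a gap of weeks to months. Sections 6.1.4 and 9.2 refer to completion of treatment without defining it, so they do not help.

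The stop date fixes a participant's time on capmatinib, the end-of-treatment visit and the 30-day safety follow-up, and the end of adjuvant imaging. It also fixes the origin of disease-free survival, which Section 12.5.1 places at the end of adjuvant capmatinib, and it feeds the trigger for the final analysis (Sections 9.2 and 12.7). Two sites could each believe they were following the text and stop on different dates.

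A smaller point concerns the C3D1 timing entry in Table 8-1, a range of 10 to 26 weeks from surgery. It looks as if week 10 were the earliest start, whereas for participants without chemotherapy it is the latest.

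**Working it through.** **Inputs.** Three years = 3 × 52 = 156 weeks, or 156 / 4 = 39 cycles of 28 days (Section 6.1.3). Maximum restart delay *d* after surgery: 10 weeks without chemotherapy (Section 6.5.1), 26 weeks with it (Section 6.2.1.1). The documents give no figure for the gap between the two readings, so there is nothing to reproduce first.

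**Formulas, in weeks after surgery.** Surgery-anchored reading: stop at 156, time on adjuvant drug 156 − *d*. Restart-anchored reading: stop at *d* + 156, time on drug 156. The difference is *d*.

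| | No chemotherapy, *d* = 10 | Chemotherapy, *d* = 26 |
|---|---|---|
| Stop, surgery-anchored | week 156 | week 156 |
| Stop, restart-anchored | week 166 | week 182 |
| Weeks on drug, surgery-anchored | 156 − 10 = 146 | 156 − 26 = 130 |
| Shortfall against 156 weeks | 10/156 = 6.4% | 26/156 = 16.7% |
| Shortfall in cycles | 10/4 = 2.5 | 26/4 = 6.5 |

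These are upper limits; an earlier restart gives a smaller gap. With 365.25-day years, three years is 156.5 weeks and the percentages are 6.4% and 16.6%.

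**Imaging.** Scans fall at weeks 0, 12, 24, 36 and 48 from the start of adjuvant treatment, then every 26 weeks (taken here as 74, 100, 126, 152, 178).

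- No chemotherapy, restart at week 10: stopping 146 weeks after restart gives 8 scans, stopping at 156 gives 9.
- With chemotherapy the count depends on when chemotherapy starts, which the documents do not fix. Assume week 6: scans fall at weeks 6, 18, 30, 42, 54, 80, 106, 132 and 158 after surgery, so 8 by week 156 and 9 by week 182.
- Assume week 4 instead: scans fall at weeks 4, 16, 28, 40, 52, 78, 104, 130, 156 and 182, so 9 and 10, counting a scan due on the stop date.

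The difference is one scan in each of these cases. With restart at week 4 and no chemotherapy it is none (9 and 9).

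**The passages side by side.** The phrase about surgery in Section 6.1.5 can set the start of the clock, or it can say when the three years of treatment are given. Section 3 uses the same order of ideas, surgery first and then three years of drug. The Table 8-1 header places its three years over columns that open at C3D1, the restart visit. The synopsis sets imaging frequency by the first year of adjuvant treatment and then by its second and third years, so it counts years of treatment, not years since surgery. That last item is weaker evidence for participants given chemotherapy, because Section 8.3.1 starts the imaging schedule with whichever adjuvant treatment comes first. On the second reading of Section 6.1.5 all the passages fit together; only the literal surgery-anchored reading creates a conflict.

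**Table 8-1 entry.** Footnote 3 is attached to that cell and gives both limits as latest dates by chemotherapy status, in agreement with Sections 6.2.1.1 and 6.5.1.

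**The case for a change.** The strongest case for a change is that a section on treatment duration should settle the duration. Its plain words set a maximum tied to surgery. A site that gave three full years after a week-26 restart would dose until week 182, past that maximum; a site that stopped at week 156 would give less than the synopsis describes. The repair would be one line, and exposure listed in days (SAP Section 2.4.1) could then be read against one planned length.

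Part of this stands. No passage states the origin of the three years, the arithmetic is right, and for one participant the gap could reach 26 weeks. It does not show that the plan produces a wrong result. The conflict needs one of two available readings, and several other passages bear on the choice. The 26-week figure requires optional chemotherapy and a restart on the last permitted day. The documents do not show that any participant reached the point where the readings part.

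**Conclusion.** The concern does not lead to a change. It is a gap in wording: Section 6.1.5 does not name the origin of its three years, and the surrounding passages supply enough context to read it. Its size is the actual restart delay, at most 10 weeks without chemotherapy and 26 weeks with it, and no scan or one scan in the cases worked.

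No planned estimate moves. SAP Section 4 records four enrolled participants, drops the planned summaries and the interim analysis, and keeps listings. SAP Section 2.7.1 leaves the secondary endpoints unanalysed, so the disease-free survival origin feeds no result. Dosing is listed as recorded, whichever stop date a site used. The Table 8-1 entry is already explained by its own footnote.

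This rests on the SAP's listings-only approach remaining in place and on the restart limits being applied as written. If a site did apply the surgery-anchored reading, Section 6.1.5 and the other passages must be reconciled by the sponsor. That is a clarification of wording, and no view is taken here on which duration is right.

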6.2 Other treatment(s)

6.2.1 Concomitant therapy

In general, the use of any concomitant medications and therapies deemed necessary for the supportive care (e.g. such as anti-emetics, anti-diarrheal) and safety of the participant are allowed except when specifically prohibited (see [Section 6.2.2](#)).

The participant must be told to notify the investigational site about any new medications he/she takes after the start of the study treatment. All medications (excluding study treatment and prior antineoplastic treatments), blood transfusions, surgeries and procedures (including physical therapy) administered within 28 days prior to the first dose administration of study drug through 30 days after the last dose of study drug will be recorded in the Concomitant Medications or Surgical and Medical Procedures eCRF, respectively. Medications include not only physician prescribed medications, but also all over-the counter medications, herbal medications, food supplements and vitamins. In addition, corticosteroid use will be documented on the appropriate eCRF until disease progression (as determined by investigator and confirmed by BIRC). Please refer to [Section 9.2](#).

The following restrictions apply during the entire duration of the study:

- No other investigational therapy should be given to participants
- No anticancer agents other than the study medication should be given to participants with exception to adjuvant chemotherapy per [Section 6.2.1.1](#)
- No radiotherapy should be given to participants

Participants are permitted to use the following medications while taking study drug:

- Oral or topical antibiotics
- Medications to prevent or treat nausea, vomiting or diarrhea
- Oxygen therapy and blood products or transfusions
- Nutritional support or appetite stimulants
- Pain medication

Each concomitant drug must be individually assessed against all exclusion criteria/prohibited medication. If in doubt, the investigator should contact the Novartis medical monitor before enrolling a participant or allowing a new medication to be started. If the participant is already enrolled, contact Novartis to determine if the participant should continue participation in the study.

All medications, procedures and significant non-drug therapies (including physical therapy and blood transfusions) administered after the subject is enrolled into the study must be recorded in the appropriate eCRF.

